# 6.4. Adverse Events

All AEs will be summarized for all treated subjects, regardless of the occurrence of a partial injection. The onset time of each AE will be compared to the time of 1st injection to determine if

Local Tolerability Study - Contraception Statistical Analysis Plan Version 2.0 TV46046-WH-10147 /1191167 the event is treatment emergent or not. Adverse events are considered treatment emergent (TEAEs) if (a) onset occurs on or after the time of first injection, or (b) an event with onset prior to the first injection but increases in severity after administration of the injection. Only treatment-emergent AEs (TEAEs) will be included in the analysis.

TEAE will be summarized in a table that presents the number and percent of subjects with any TEAE, with any serious TEAE, and with any TEAE leading to discontinuation from the study. All TEAEs will be summarized in frequency tables by MedDRA version 21.1 System Organ Class (SOC) and preferred term. Only adverse events which can be ascribed to a particular treatment group (e.g., ISRs that meet the definition of an AE) will be compared between groups using Fisher's Exact tests.

A listing of all AEs will include treatment group (where possible), verbatim AE description, preferred term and SOC, duration, relatedness to product (where relatedness is possible to ascribe), seriousness, severity, outcome, and whether the subject withdrew from the study as a result of the AE.

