1.4. Study Design Rationale

1.4.1. General Study Design Rationale

Interim data from Study TV-46046-WH-10075 suggested that the subcutaneous administration of TV-46046 may be associated with a higher rate of ISRs than Depo-subQ 104. The lack of a direct comparison, the small sample size and the potential differences in ISR ascertainment complicate the interpretation of these results. The study described here will allow assessment and direct comparison of local tolerability between 120 mg/0.3 mL of TV-46046 and the reference drug, Depo-subQ 104. Inclusion of 60 mg/0.3mL of the 1:1 saline-diluted TV-46046 will enable investigation of a potential dose-dependent effect.

The proposed study is a single-group cross-over design in which 24 women will receive one of each of the four subcutaneous study injections in different quadrants of the abdomen approximately 1 hour apart (considered to be sufficient to eliminate carry-over effect of pain from previous injection). Each woman will serve as her own control to minimize the variability of treatment comparisons. Women will be randomized to one of 24 possible injection sequences (one subject per sequence) to counterbalance potential effects of injection order or abdominal quadrant on outcomes.

This study will recruit healthy subjects to eliminate confounding factors (comorbidities, comedications). Since TV-46046 is a hormonal contraceptive, only women will be enrolled into the study. Since the contraceptive dose and duration of TV-46046 action are unknown, enrollment will include women who are in menopause, or are premenopausal and are not pregnant, not wanting to become pregnant in the next 18 months, or at a low risk of pregnancy because they are sterilized, in an exclusively same-sex partnership, abstinent, in a monogamous relationship with a vasectomized partner, using non- hormonal IUD, or consistently using condoms.

In the ongoing TV46046-WH-10147 study, several cases of hypopigmentation had a later onset (ie, approximately 6 months post-injection) than observed in Study TV46046-WH-10075. In order to identify any late onset ISRs, subjects who have exited the study at Month 6 with no new or ongoing ISRs and who agree to return for a single follow-up visit between Months 9 and 12, will undergo ISR, adverse event, and concomitant medication evaluation, and vital sign and weight measurements at that time (see Section 3.4.5 for more detail).

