8.1. Sample Size and Power Considerations

The study size of 24 subjects, each of whom will receive all four treatments (one per abdominal quadrant), will provide at least 80% power to detect differences in the rates of ISRs among groups of the magnitude (>40%) observed in recent non-comparative studies of TV-46046 and Depo-subQ 104 (see Table 3). Although not designed to obtain precise estimates of less frequent ISR rates (eg, injection site discoloration [hypopigmentation]), there is a high (>90%) probability of detecting one or more specific ISR types per treatment if the true rate of such events is at least 10%. No randomized subjects will be replaced. However, if more than two subjects fail to receive all four injections or discontinue before Month 6, then additional subjects may be enrolled to help ensure that there are at least 22 subjects who complete the treatment sequence and are evaluable for at least 6 months.

	Injection Pain	Redness	Injection Site Discoloration (Hypopigmentation)	Any Adverse Event	Reference
TV-46046 (Study #TV-46046-WH- 10075; IND 126249)	8/12 (66.7%)	9/12 (75.0%)	2/12 (16.7%)	9/12 (75.0%)	Ongoing PK/PD
Depo-subQ 104 (Study #702179; IND 127097)	3 /18 (16.7%)	1/18 (5.5%)	0/18 (0%)	2/18 (11.1%)	Ongoing PK/PD

Table 3:ISR Rates (per injection)

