8.6. Analysis of Primary Endpoints

8.6.1. Local Tolerability

The primary ISR endpoint will be assessed at least twice on Day 0: immediately after [ie, as soon as possible but no later than 10 minutes upon removing the needle] and again 1 hour after each of the four injections), at Days 1, 3, 7 and 14, at Months 3 and 6, and at additional visits, if indicated. Prior to the interim and/or final analysis, FHI 360's clinician will conduct a blinded review of ISR outcome information (recorded on study CRFs and clinical notes, if necessary) to assess adherence to protocol definitions; proper ISR and/or adverse event documentation and reporting; and potential redundant endpoints. All documented ISRs will be summarized for each treatment group using frequencies and percentages. The frequency of ISRs as well as ISRs that meet the per-protocol definition of an adverse event, will be compared between the treatment groups.

If there are sufficient numbers of ISRs to warrant the use of asymptotic methods, pair-wise treatment odds ratios for ISR (there are 6 possible comparisons among 4 treatment groups) will be assessed using logistic regression models with generalized estimating equations and robust

variance estimation to account for the correlated nature of the data. The primary model for such ISRs will only include effects of treatment group. An exchangeable working correlation structure will be used to estimate covariance parameters. Parameter estimates, standard errors, 95% confidence intervals, Z scores, and p-values for parameter estimates will also be produced. In addition, if the population is sufficiently heterogeneous with respect to these factors, exploratory analyses may be performed to assess effect of injection order, age and race. For less frequent ISR types, differences between groups will be assessed using exact McNemar's tests (separately for each of the 6 possible treatment comparisons). A final determination of whether the asymptotic method is appropriate will be made by the lead statistician based on observed correlation structures and event rates, blinded to treatment group prior to database lock and will be conducted at the nominal two-sided 0.05 significance level with no adjustment for multiple comparisons.

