# 6.2. Local Tolerability

The primary ISR endpoint will be assessed at least twice on Day 0: immediately after [ie, as soon as possible but no later than 10 minutes upon removing the needle] and again 1 hour after each of the four injections; on Days 1, 3, 7 and 14; at Months 3 and 6, and at additional visits, if indicated. The frequency with which subjects experience any ISR as well as those experiencing each category of ISR documented on the case report form (i.e., redness, swelling, itching, bleeding, bruising, skin discoloration, atrophy/dimple) will be summarized by treatment group, as well as ISRs that meet the per-protocol definition of an AE. Data listings will include time to onset, duration, and resolution of the ISR.

For an ISR type, if there are sufficient numbers of ISRs to warrant the use of asymptotic methods, pair-wise treatment odds ratios (for all 6 possible comparisons among 4 treatment groups) will be assessed using logistic regression models with generalized estimating equations and robust variance estimation to account for the correlated nature of the data. The primary model will only include effects of treatment group. An exchangeable working correlation structure will be used to estimate covariance parameters. Parameter estimates, standard errors, 95% CIs, Z scores, and p-values for parameter group comparisons will also be produced. Exploratory analyses may be performed to assess effect of injection order, age and race if the population is deemed sufficiently heterogeneous with respect to these factors (based on opinion of lead statistician, in blind review of data). For less frequent ISR types (i.e., those determined not to be amenable to asymptotic method analysis), differences between groups will be assessed using exact McNemar's tests (separately for each of the 6 possible treatment comparisons). A final determination of whether the asymptotic method is appropriate will be made by the lead statistician based on observed correlation structures and event rates, blinded to treatment group prior to database lock and unblinding. In particular, if the expected coverage error of 95% confidence intervals is predicted to be below 90% (as determined in simulation studies), then the exact method will be used.

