# 6.3. Injection Site Pain

NRS pain scores for assessments on the day of injection (Day 0) will be summarized by treatment group in frequency tables, separately for pain measured immediately after injection and at 1 hour after injection. If an appropriate distribution of pain scores can be identified in blinded review (e.g., negative binomial or Poisson), then generalized linear models with exchangeable working correlation structure to account for correlated data will be used to compare treatment groups. The analysis model will only include effects of treatment, but exploratory analyses will be performed to assess effects of injection order, age, and race. If the dispersion of NRS scores is not amenable to parametric regression methods, then rank-order, permutation tests will be used to compare treatment groups (excluding any subjects who did not receive both injections being compared).

Approximately 1 hour after completing their sequence of the four treatments, each subject will also be asked to rank the injections according to overall pain from least [1] to most [4] painful. The ranking of treatment group pain will be summarized in bar charts and frequency tables, restricted to subjects who received all four injections. Differences in ranking of most painful injection will be assessed using an exact multinomial test for homogeneity across groups. If a subject cannot rank all of her injections from least to most painful, or cannot uniquely identify which injection was most painful, then her responses will be appropriately weighted across groups (e.g., if a subject ranks all 4 treatments as equally most painful, then that subject will contribute a score of 0.25 to each group when assessing distribution of most painful injection).

The proportion of subjects with unsolicited reports of injection site pain at one or more follow-up visits after Day 0 will be tabulated and compared between treatment groups using exact, pairwise McNemar tests.

Listings of pain score data will include subjects who received partial injections.

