# 8. CHANGES TO ANALYSES SPECIFIED IN PROTOCOL V1.0

# 8.1. Changes from V1.0 of SAP, prior to interim analysis

In consultation with the SRC and in a completely blind data review, the decision was made on April 26th 2019 to enroll 3 additional subjects because 3 of the planned total of 24 received only partial injections of one of the drugs. Based on this consultation, the decision was made to exclude partial injections from the primary safety analysis and to entirely exclude subjects who experienced a partial injection from the secondary pain score analysis. All subjects, regardless of any partial injections, remain included in the assessment of overall safety per section 1.2.2.2. Demographic data will be summarized for both the Treated Analysis Set and the subset of subjects who received no partial injections of drug.

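### SAP 6.4 compares adverse events between injection sites on the same women with Fisher's exact test, which treats the sites as independent groups

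*SAP*

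**What the plan says.** SAP 6.4 limits between-group testing of adverse events to those that can be tied to one injection, and names the test: "e.g., ISRs that meet the definition of an AE) will be compared between groups using Fisher's Exact tests". The section keeps everyone who was treated: "All AEs will be summarized for all treated subjects, regardless of the occurrence of a partial injection".

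The design is within-woman. Protocol 8.1 describes 24 subjects, "each of whom will receive all four treatments (one per abdominal quadrant"), and Protocol 1.4.1 gives the reason: "Each woman will serve as her own control to minimize the variability of treatment comparisons".

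The other yes/no comparisons of injection sites respect that pairing. SAP 6.2 uses logistic regression with generalized estimating equations (GEE) and robust variance where counts allow. For less frequent reaction types, "differences between groups will be assessed using exact McNemar's tests". SAP 6.3 has follow-up pain reports "compared between treatment groups using exact, pairwise McNemar tests". Protocol 8.6.1 says that "ISRs that meet the per-protocol definition of an adverse event, will be compared between the treatment groups", and the only methods it names are GEE and exact McNemar.

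Protocol 8.7.2 names no between-group test for adverse events. SAP 8 does not list Fisher's test as a change from the protocol, and the SAP introduction lets the SAP prevail where the two documents differ.

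**The concern.** Fisher's test takes its reference distribution from two independent samples. Here both columns of the 2x2 table come from the same women, and the test sees only the two totals. It cannot tell whether the women who reacted at one site are those who reacted at the other, which is the information the own-control design was meant to collect.

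The SAP may also analyse the same events twice. SAP 6.2 lists injection site reactions (ISRs) that meet the adverse event definition among its outcomes, so they could receive a paired p-value there and an unpaired one in 6.4. The data would differ too, since 6.2 drops partial injections and 6.4 keeps them. Nothing says which result is the planned one.

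In a tolerability study the main risk is a missed difference in local harm. If reactions tend to occur in the same women, Fisher's test becomes very conservative and loses power when events are common.

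**Working it through.** **The plan's own figures.** None depends on the 6.4 test, and both sample size statements reproduce.
- Power of at least 80% for a difference above 40 points: the independent-groups formula at 70% v 30%, n = 24, gives z = (0.40×√24 − 1.96×√0.50)/√0.42 = 0.885, so power is 81.2%.
- Chance of seeing at least one event at a 10% rate: 1 − 0.9^24 = 92.0%.

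**Inputs.**
- Two-sided 0.05 without multiplicity adjustment (Protocol 8).
- 24 pairs as planned, or 27 if the three added women (SAP 8.1: "to enroll 3 additional subjects because 3 of the planned total of 24 received only partial injections of one of the drugs") received both injections being compared.
- The documents give no within-woman correlation. A range of 0 to 0.8 is assumed, on a latent bivariate normal scale.
- Event rates are assumptions, except those taken from Protocol Table 3.

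**Formulas.** Let b and c be the numbers of women with the event only at the first site and only at the second.
- Exact McNemar: p = 2 × P(X ≥ max(b, c)), X ~ Binomial(b + c, ½), capped at 1.
- Fisher: the two-sided hypergeometric p-value from the two totals, n per group.

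**Same totals, different pairing.**

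| Totals | Both / first only / second only / neither | Fisher p | Exact McNemar p |
|---|---|---|---|
| 14 v 8 of 27 | 8 / 6 / 0 / 13 | 0.166 | 2 × (½)^6 = 0.031 |
| 14 v 8 of 27 | 0 / 14 / 8 / 5 | 0.166 | 0.286 |
| 10 v 4 of 24 | 4 / 6 / 0 / 14 | 0.111 | 0.031 |
| 5 v 0 of 24 | 0 / 5 / 0 / 19 | 2 × C(24,5)/C(48,5) = 0.0496 | 2 × (½)^5 = 0.0625 |

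The last row goes the other way: exact McNemar cannot reach 0.05 with fewer than six discordant pairs.

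**Type I error and power.** Every paired 2x2 table was enumerated, and the probabilities of tables with p < 0.05 were summed for each test.

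| Rates | Correlation | Fisher, 24 pairs | McNemar, 24 pairs | Fisher, 27 pairs | McNemar, 27 pairs |
|---|---|---|---|---|---|
| 30% v 30% (type I error) | 0.6 | 0.5% | 1.3% | 0.4% | 1.6% |
| 50% v 20% | 0 | 49% | 46% | 55% | 52% |
| 50% v 20% | 0.3 | 49% | 53% | 55% | 60% |
| 50% v 20% | 0.6 | 49% | 63% | 55% | 71% |
| 50% v 20% | 0.8 | 48% | 72% | 55% | 81% |
| 20% v 2% | 0 to 0.8 | 36–39% | 25% | 29–32% | 33–36% |

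The order at 20% v 2% reverses between 24 and 27 pairs because 5 v 0 is just significant under Fisher at 24 (0.0496) and just misses at 27 (2 × C(27,5)/C(54,5) = 0.051).

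Over equal rates of 5% to 50% with 24 pairs, the maximum type I error of Fisher's test is 2.9%, 1.5%, 0.6% and 0.15% at correlation 0, 0.3, 0.6 and 0.8.

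**The case against.** The other side has several fair points.

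- **A paired analysis may already exist.** On one reading, Protocol 8.6.1 and SAP 6.2 cover ISRs at adverse event level, and 6.4 is a supportive table for a secondary safety endpoint. This stands in part. The primary endpoint excludes injection site pain, however, so pain that reaches adverse event level (a score of 7 to 10, Protocol 5.2.1) is not covered by 6.2.
- **No excess of false positives.** This stands for non-negative correlation. Exact McNemar is also well below 5%, and at 10% v 10% with correlation 0.3 and 24 pairs it is the more conservative test (0.40% v 1.05% for Fisher).
- **Fisher is sometimes more powerful.** This stands, as the table shows at correlation 0 and at sparse rates with 24 pairs.
- **At the planning rates the choice hardly matters.** At the Table 3 any-adverse-event rates (75% v 11.1%) both tests have at least 99.5% power. At the injection pain rates (66.7% v 16.7%, 24 pairs) Fisher has 93.5–97.0% and McNemar 91.6–99.6%. This holds for the TV-46046 v Depo-subQ 104 contrast. Table 3 gives no rates for the diluted or placebo injections, where differences may be smaller.
- **Using the 6.2 approach (GEE where counts allow) would match that section better.** That would also be a paired analysis. Exact McNemar is already the SAP 6.3 convention and works at any event count, so it is the simpler choice.

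These points limit the impact. None makes an independent-samples test right for paired data.

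**Conclusion.** The concern holds. SAP 6.4 names a test for independent groups in a design where every woman contributes to every group, and it departs without explanation from SAP 6.2, SAP 6.3 and Protocol 8.6.1.

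The effect is confined to the adverse event comparison. The primary any-ISR analysis, the pain score analysis and the sample size are untouched. Within that comparison the choice of test can change a conclusion, and at 50% v 20% the power lost by Fisher's test with 24 pairs runs from about 4 points at correlation 0.3 to 24 points at 0.8. Those losses rest on assumed rates and an assumed positive correlation. With none, Fisher is about 3 to 4 points ahead at the same rates.

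The case for change is therefore a correct reference distribution and a consistent SAP, without a promise of more power in every setting. It should be fixed, but it does not threaten the main result.

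**What to change.** In SAP 6.4, replace Fisher's exact tests with exact, pairwise McNemar tests among women who received both injections being compared. Keep the section's population: all treated women, with partial injections included. State that this is the planned test for ISRs at adverse event level, and label any 6.2 result for those events as coming from a different analysis set, because it excludes partial injections.

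The cost is one or two sentences in 6.4, a label on any 6.2 table of these events, and a change of test in one table program. Data collection and the population analysed stay as they are.

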#### 6.5. Vital Signs and Body Weight

Pulse rate, respiration rate, systolic/diastolic blood pressure, body weight and temperature will be summarized using descriptive statistics by study visit as well as listed by subject and visit when assessments take place. Change from baseline to Month 6 in vital signs and body weight will also be summarized descriptively. Data will be summarized for all treated subjects, regardless of the occurrence of a partial injection.

#### 6.6. Concomitant Medications

Concomitant medications include medications that were taken at any time during the study, up to the end of study as defined in the study protocol. All concomitant medications will be coded according to the World Health Organization (WHO) drug dictionary (WHO Drug Global B3/C3). The use of concomitant medications will be summarized by therapeutic class and category with descriptive statistics. Subjects are counted only once in each therapeutic class, and only once in each CM category. Data will be summarized for all treated subjects, regardless of the occurrence of a partial injection

Statistical Analysis Plan Version 2.0

## 7. STATISTICAL SOFTWARE

All data listings, summaries, and statistical analyses will be generated using SAS® version 9.4 or later.

# 8. CHANGES TO ANALYSES SPECIFIED IN PROTOCOL V1.0

# 8.1. Changes from V1.0 of SAP, prior to interim analysis

In consultation with the SRC and in a completely blind data review, the decision was made on April 26th 2019 to enroll 3 additional subjects because 3 of the planned total of 24 received only partial injections of one of the drugs. Based on this consultation, the decision was made to exclude partial injections from the primary safety analysis and to entirely exclude subjects who experienced a partial injection from the secondary pain score analysis. All subjects, regardless of any partial injections, remain included in the assessment of overall safety per section 1.2.2.2. Demographic data will be summarized for both the Treated Analysis Set and the subset of subjects who received no partial injections of drug.

# 9. TABLES, FIGURES, AND LISTINGS

Table shells are maintained in a separate document.

